### **8.2.2 Serious Adverse Event**

Serious Adverse Event (SAE): defined as any AE that (at any dose):

- Results in death
- Is life-threatening. NOTE: The term "life-threatening" refers to an event in which the subject was at risk of death at the time of the event; it does not refer to an event which hypothetically might have caused death if it were more intense
- Requires inpatient hospitalization or prolongs existing hospitalization
- Results in persistent or significant disability/incapacity
- Is a congenital anomaly/birth defect
- May jeopardize the subject or may require intervention to prevent one of the outcomes listed above. Medical and scientific judgment should be exercised in deciding if these events should be considered serious. Examples of such events are intensive treatment in an emergency room or at home for allergic bronchospasm, blood dyscrasias or convulsions that do not result in hospitalization, or development of drug dependency or drug abuse.

In addition, an AE that results in overdose or produces congenital abnormality or cancer is always considered an SAE.

A subject admitted to a hospital as a result of an AE, even if released on the same day, would qualify for inpatient hospitalization. An emergency room visit that results in admission to the hospital would also qualify for inpatient hospitalization. However, emergency room visits that do not result in admission to the hospital would not qualify for inpatient hospitalization and, instead, should be evaluated for one of the other criteria for SAEs (e.g., life-threatening AE or medically significant event).

Hospitalization scheduled before a subject enrolls in the study is not the result of a treatment-emergent AE, and therefore events leading to such hospitalization will not be considered study AEs or SAEs. During the study, if a subject has elective surgery for a condition present at screening into the study, and the condition did not worsen during the study, the reason for elective surgery, and resulting hospitalization (if applicable), should not be considered or reported as an SAE. Surgery or hospitalization should always be reported as an outcome of an AE. For AEs that result in persistent or significant disability/incapacity, refers to a substantial disruption of a subject's ability to carry out normal life functions.

The investigator must also submit documentation of the following to the Institutional Review Board, Ethics Committee, or Research Ethics Board (collectively referred to as an IRB):

- Site-specific SAEs and follow-up: The type of serious event that must be submitted (e.g., all or only suspected), as well as the required timing of submission (e.g., within 10 days of occurrence), is defined by the IRB and regulations/guidance from regulatory authorities.
- Any documentation provided by the Sponsor regarding reportable SAEs from the study: The Sponsor will provide documentation of reportable events to the investigator, as specified in [Section 8.7](#).

The investigator should ensure that the subject receives appropriate medical treatment and that the subject is followed up until the SAE resolves or becomes chronic, as defined in [Section 8.4](#).

### **8.3 Adverse Event Descriptions**

#### **8.3.1 Intensity**

The intensity of AEs will be characterized as mild, moderate, or severe, as follows:

- Mild: Usually transient, requiring no special treatment, and does not interfere with the subject's daily activities
- Moderate: Introduces a low level of inconvenience or concern to the subject and may interfere with daily activities, but is usually ameliorated by simple therapeutic measures
- Severe: Significantly interferes with a subject's usual daily activities and requires systemic drug therapy or other treatment, if available

#### **8.3.2 Relationship to Study Treatment**

The causal relationship to study drug or treatment will be determined by the investigator according to best medical judgment, as follows:

- Suspected: There is a reasonable possibility that the AE is associated with use of the study treatment, such as a temporal relationship of the event to study treatment administration, or

when other drugs, therapeutic interventions, or underlying conditions do not provide a sufficient explanation for the observed event

- Not suspected: A relationship between the AE and the study treatment can reasonably be ruled out based on lack of any temporal relationship of the event to study treatment administration, or when the subject's underlying condition, medical history, or other therapy provide sufficient explanation for the observed event.

#### **8.4 Follow-up for Adverse Event Definitions**

Throughout the study to the final study contact, all AEs will be followed until they resolve or become chronic (as judged by the investigator).

At the final study visit, new AEs, as well as follow-up information for continuing AEs, will be recorded in the CRF and source document. If an SAE (defined in [Section 8.2.2](#)) is unresolved at the final study visit, it will be followed by the investigator until it resolves or becomes chronic (as judged by the investigator). Follow-up data for such SAEs will be recorded in the source document and reported to the safety monitors (refer to [Section 8.7.2](#)). Non-serious ongoing AEs will be followed beyond the final study visit at the discretion of the investigator and recorded in the source documents.

#### **8.5 Pregnancy Follow-up**

If a subject becomes pregnant during the study, the investigator must inform the Sponsor and collect follow-up data regarding the pregnancy, birth, and status of the child. The Sponsor will provide special CRFs for data collection in the case of pregnancy. Follow-up should be continued until study close-out at the study site. After close-out, the Sponsor's Safety designee will continue to obtain follow-up information.

Pregnancy should be recorded as a protocol deviation. Pregnancy is not an AE; however, any complication related to pregnancy would be considered an AE.

#### **8.6 Reporting of Technical Complaint**

##### **8.6.1 Definitions**

A quality complaint is one that is received in writing, electronically, or orally that involves the use or attempted use of a Travoprost Evolute® plug that identifies any defect in the physical properties of the drug product (color, precipitates, viscosity, etc.) or its packaging. Technical complaints also include any identified customer dissatisfaction with the physical characteristic(s) of the study product (dispensing characteristics, labeling, packaging, etc.).

##### **8.6.2 Reporting of Technical Complaints**

Any technical complaint should be reported by fax to the Sponsor's Chief Scientific Officer (contact information below) within 24 hours. The complaint report should include the following information:

- Name of the study product
- Strength of study product
- Batch/lot number of study product
- Investigator name, study site name, and contact number
- Date the complaint occurred
- Brief description of the complaint
- Identity of any other investigational or commercial devices involved.
- Study subject or another individual involved (yes/no):
  - If yes and a study subject, the investigator should report whether any AEs were associated with the complaint (yes/no; if a subject AE was associated with the complaint, refer to Sections 8.6 & 8.7 and attach the AE CRF page to the complaint)
  - If yes and another individual, the investigator should describe the situation and any ill effects on the health of the individual
  - If no, in the investigator's judgment, the investigator should report whether the complaint could reasonably cause an SAE if it recurred under circumstances that did involve a study subject or other person (yes/no).

The study product and associated packaging that initiated the complaint should be returned to the Chief Scientific Officer (address below) for analysis.

Mati Therapeutics Inc.  
Attn: Chief Scientific Officer  
[name]  
[name]  
Burnaby, BC  
[name]  
[contact]  
[contact]

Any complaint about a study product must be reported regardless of whether the defect or deficiency had any effect on a subject or on study personnel.

#### 8.6.3 Punctal Plug Delivery System Serious Adverse Events and Technical Complaints

The Sponsor will evaluate all SAE reports and technical complaints received in the study to determine if the report meets the definition of an unanticipated ADE. Unanticipated ADEs are defined as follows:

- Any serious adverse effect on the health or safety or any life-threatening problem or death caused by, or associated with, a device, if that effect, problem, or death was not previously

identified in nature, severity, or degree of incidence in the investigational plan or application or any other unanticipated serious problem associated with a device that relates to the rights, safety, or welfare of a subject.

If the Sponsor determines that any SAE or technical report is an unanticipated ADE, an investigation will begin immediately. The Sponsor will inform the investigator of any additional reporting requirements beyond those stated in Sections [8.6](#) & [8.7](#) as applicable.

If the Sponsor determines that an unanticipated ADE presents an unreasonable risk to a subject, the Sponsor will terminate the study as soon as possible. Termination will occur no later than five working days after the Sponsor makes this determination and no later than 15 working days after the Sponsor first received notice of the effect. The Sponsor will report the results of any investigations to the FDA and to investigators, who will also submit the reports to his/her IRBs, within 10 working days after the Sponsor first received notice of the effect.

#### 8.6.4 Anticipated Adverse Event

The following is a list including, but not limited to, ocular adverse events that are anticipated. Any event that is unlikely but anticipated must have an adverse event form completed and reported to Mati Therapeutics Inc. ([Section 8.7](#) for reporting details).

##### Listing of Anticipated Ocular Adverse Events

###### DRUG:

Incidence rate 30-50%: Hyperemia (\*Hyperemia in IZBA controlled studies noted at 12%)

Incidence rate 5-10%: Decreased VA, Eye Discomfort, Foreign Body Sensation, Pain, Pruritus

Incidence rate 1-4%: Abnormal Vision, Blepharitis, Blurred Vision, Cataract, cells, Conjunctivitis, Corneal Staining, Dry Eye, eye disorder, Iris Discoloration, Keratitis, Lid Margin Crusting, Ocular Inflammation, Photophobia, Subconjunctival Hemorrhage, Tearing

###### DEVICE:

The main risks of commercial silicone punctal plugs are ocular discomfort, epiphora (watery eyes), loss of plug (extrusion), ocular inflammation, and subconjunctival hemorrhage. Less common, but serious, side effects include but are not limited to pyogenic granuloma, damage to the muscle at the opening of the punctum, canaliculitis or migration of the plug into the canalicula (requiring irrigation or surgery)

**NOTE:** Patient treated with an ophthalmic solution of travoprost should be informed of the potential for increased brown pigmentation of the iris, periorbital and/or eyelid tissue, and increase growth of eyelashes in the treated eye

#### 8.7 Reporting Procedures

AEs/ADEs that occur from Visit 2 through completion of the end-of-study visit must be documented. The Investigator will assess the AE/ADE severity and relationship to the travoprost Evolute®. The Investigator will follow the progress of the study subject until the AE/ADE either resolves or becomes medically stable. Treatments and medications required for treatment must be recorded.

All AEs/ADEs, regardless of severity and whether or not attributed to the drug delivery device are to be reported to Mati Therapeutics Inc. AEs/ADEs are also to be reported to the site IRB per the IRB's reporting requirements.

#### 8.7.1 Adverse Event Reporting

For each reported AE, investigators should record the following on the appropriate CRF and in the subject's source documents: whether an AE is serious (yes/no), the date of onset, date resolved (date or ongoing), duration (minutes/hours/days), frequency (single/intermittent), severity (mild/moderate/severe), relationship to study treatment (suspected/not suspected), and if treatment was required (medication prescribed, stopped treatment, etc.).

An adverse event that is not serious or related to the study drug or drug delivery device is to be reported to the designated Medical Monitor within 10 working days of the Investigator first becoming aware of the event. Notification will occur by recording on the appropriate CRF(s), scanning and email or faxing the CRF(s) of the visit in which the event is first noted. An adverse event is also to be reported to the reviewing IRB/IEC per their reporting requirements.

#### 8.7.2 Serious Adverse Event Reporting

Any severe, serious or unexpected AE occurring during or within 15 days after the completion of the study, regardless of cause(s) or relationship to the study drug or the drug delivery device, an initial report must be made immediately (within 24 hours) once becoming aware of the event by telephone, facsimile, or email to the study Medical Monitor, [name] or the Study Monitor, [name] (see contact information below).

The Investigator must complete an SAE Report Form and send it with other relevant pages of the CRF to the designated Medical Monitor within 24 hours of the initial discovery of the event. The Investigator will also compile with urgent priority other relevant documentation (copies of test results, hospital discharge summary, autopsy report, etc.) and send this information to the designated Medical Monitor. Any SAE will be reported to the Investigator's IRB/IEC per their reporting requirements.

All SAEs will be reported to:

[name]  
Medical Monitor  
Mati Therapeutics Inc.  
email: [contact]  
Phone: (Office): [contact]  
Phone: (Cell) [contact]  
[contact]

[name] (back up contact)  
Study Monitor  
D'Ellis Group, Inc.  
email: [contact]  
Phone: (Office): [contact]  
Phone: (Cell) [contact]

### 8.7.3 Unanticipated Problem Reporting

If during the study an adverse event occurs that may reasonably be regarded as study drug and/or study-device-related and was not previously expected in nature, severity, or degree of incidence in the investigation plan, the Investigator is to report the unanticipated adverse event to the designated Medical Monitor within 48 hours, and to the Investigator's IRB as soon as possible, but no later than 10 working days, after learning of the event as required by 21CFR812.

### 8.7.4 Events of Special Interest

Not Applicable

## 8.8 Halting Rules

Collaboration between representatives of Mati Therapeutics Inc., Investigators and statisticians may stop the study if there is evidence of a lack of safety or efficacy associated with the study drug/device or if there is sufficient evidence of efficacy to warrant phase III testing.

## 8.9 Safety Oversight

This study will utilize a Medical Monitor for safety monitoring. The Medical Monitor will review and assess any reports of adverse events/adverse device events and, if necessary, to discuss these with the reporting Investigator(s). The medical monitor will also be available to answer all questions from Investigators.

## 9 CLINICAL MONITORING

Mati Therapeutics Inc. representative will ensure that the investigation is conducted in accordance with the following:

- a. GCPs as specified in ICH E6 (R2) and E8 (8.2) and 21 CFR. Parts 50, 54, 56, 312 and 812
- b. The signed Investigators' Agreement
- c. The signed IRB approved protocol for the study
- d. Any conditions imposed by the IRB
- e. The requirements of the regulations for the Protection of Human Patients (21CFR50) and all other applicable regulations

Prior to initiation of the study at a site, a Mati representative will conduct a visit with the Investigator(s) and the study staff to ensure the following

- a. The Investigator understands the investigational status of the study material and the requirements for its accountability

- b. The Investigator understands the protocol and understands and accepts his/her obligations in conducting the clinical investigation
- c. The Investigator has adequate facilities for conducting the study, and equipment and instrumentation required by the protocol
- d. The Investigators and his/her staff have sufficient time and access to an adequate number of subjects to conduct the clinical investigation.

During the course of the investigation, a Mati representative may conduct periodic site visits and maintain telephone contact with the Investigators and his/her staff to verify that the study is being conducted in accordance with the protocol, and with any specific conditions of the IRB and clinical requirements. At such visits, a Mati representative will:

- a. Verify that informed consent has been obtained and documented for each study subject, in accordance with 21 CFR parts 50 and 56, and the requirements of the overseeing IRB and the Sponsor.
- b. Review and compare CRFs to source records and supporting documents to ensure that data recorded on the CRFs are complete, accurate, and legible
- c. Verify that any corrections to the CRFs are made with a single line strike-through of the incorrect entry, and entry of the correct information adjacent with initials of the individual making the correction and date of corrected entry
- d. Verify that there are no data omissions and that any study subject withdrawals are documented.
- e. Review CRFs and source records for any unanticipated AEs/ADEs, and ensure that the Investigators are complying with FDA and Sponsor requirements for reporting AEs/ADEs and SAEs/SADEs.
- f. Verify that the Investigator(s) is carrying out the agreed upon activities and has not delegated them to unauthorized staff and that the facilities and staff continue to be acceptable for the study.
- g. Verify the Investigator(s) is properly tracking study inventory and is accounting for the disposition of all study devices.
- h. Prepare and maintain records of each site visit, significant telephone discussion, and written communications with the site. These records will include such information as:
  - i. Date, name, and address of the Investigator(s) and names of other staff members present at each meeting
  - ii. A summary of the findings of the visit
  - iii. A statement of any action taken by a Mati representative or Investigator(s) to correct any deficiencies noted.

## 10 STATISTICAL CONSIDERATIONS

### 10.1 Statistical and Analytical Plans

The primary analysis population will be an ITT (Intent-to-Treat) analysis for all study subjects who had the lower puncta of each eye inserted with a study punctal plug and had no major protocol violations. Individual study subjects or individual visits may be excluded if a major protocol violation occurs (such as violation of inclusion/exclusion criteria or non-compliance with protocol requirements that can potentially have significant impact on study outcomes).

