#### 5.4.3 Handling of Study Subject Termination, Discontinued or Disqualified

##### 5.4.3.1 Handling of Terminated Study Subject

A terminated study subject will return to the clinic for an end of study safety evaluation and the removal of his/her punctal plugs. A terminated study subject will receive appropriate treatment at the discretion of the Investigator. Notification of termination will be clearly documented on the appropriate Case Report Form. A terminated study subject is considered to have completed the study and **will NOT be replaced**.

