## 7.10 Rescue Medication(s)

### 7.10.1 Administration of a Rescue Medications

A subject with an elevated IOP (>34 mmHg) or undue medical risk in either eye should be prescribed his/her glaucoma regimen they were using prior to entering the study. The use of a rescue medication will be considered prohibited medication and will be considered a protocol deviation and the study subject will be terminated from the study. Reason for termination on the exit form should be listed as "due to lack of efficacy".

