### 10.4 Description of Statistical Methods

#### 10.4.1 General Approach

Descriptive statistics (i.e., mean, standard deviation, etc.) will be provided for all continuous variables and frequency distributions will be generated for all categorical variables collected in this study. Analyses of the intent-to-treat (ITT) data set, will include all data from all subjects with a recorded screening visit IOP OU. Per protocol (PP) analyses dataset, will exclude data from subjects or visits with significant protocol deviations (e.g., IOPs obtained before 8:00 AM and after 10:00 AM will be excluded).

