#### 10.4.7 Planned Interim Analyses

Data will be analyzed on an ongoing basis. The final analyses will be completed after the last study subject has completed his/her final visit and the study database has been closed.

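### The primary set that section 10.1 calls ITT works like a per-protocol set, section 10.4.1 gives the ITT label to a different set, and the exclusions have no closed list, decision-maker or date

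*Combined protocol and SAP*

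**What the plan says.** Section 10.1 is the only text that names a primary analysis population. It labels that population ITT and restricts it to subjects who had both lower puncta "inserted with a study punctal plug and had no major protocol violations". It then adds: "Individual study subjects or individual visits may be excluded if a major protocol violation occurs". The examples given are eligibility violations and "non-compliance with protocol requirements that can potentially have significant impact on study outcomes".

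Section 10.4.1 uses the same label differently: "Analyses of the intent-to-treat (ITT) data set, will include all data from all subjects with a recorded screening visit IOP OU". It goes on to a PP set that "will exclude data from subjects or visits with significant protocol deviations". Its one example is an IOP taken outside 8:00 to 10:00 AM.

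On timing, section 10.4.7 says "Data will be analyzed on an ongoing basis", with final analyses after the last visit and closure of the database. Section 4.1 describes the study as open-label, and section 10.6 marks measures to minimise bias as not applicable.

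On rescue, section 7.10.1 states that "use of a rescue medication will be considered prohibited medication and will be considered a protocol deviation and the study subject will be terminated", with lack of efficacy as the recorded reason. Section 5.4.3.1 begins its rule with "A terminated study subject is considered to have completed the study and" and goes on to rule out replacement. Section 5.4.2.1(f), by contrast, makes a user of prohibited medication a discontinued subject, and section 5.4.3.2 has discontinued subjects replaced.

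**The concern.** An analyst who follows section 10.1 would produce an estimate with violators removed and report it as ITT. A reader of the report would take the label to mean that plugged subjects were kept whatever happened to them afterwards.

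The second problem is discretion. The exclusion rule works by example, is optional, and turns partly on possible impact on outcomes. Nobody is named to apply it and no date is set. With IOP visible to everyone and analysed as it arrives, exclusions could be decided after their effect on the mean is known.

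The subjects most likely to matter are those who leave for lack of efficacy, because rescue is classed as a protocol deviation. A pilot is run for its estimate, and section 8.8 allows the study to stop either for lack of efficacy or for enough efficacy to move to phase III. The set behind that estimate should not be open to choice.

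**Working it through.** There is no sample size, power or alpha in the plan to reproduce. The check is a comparison of texts, followed by an illustration.

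**Step 1. The sets side by side.**

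| Feature | 10.1 primary set, labelled ITT | 10.4.1 ITT | 10.4.1 PP |
|---|---|---|---|
| Both plugs inserted | required | not required | not stated |
| Subjects or visits with violations | first sentence requires none that are major; second makes exclusion optional | kept | excluded if the deviation is significant |
| Examples | eligibility; non-compliance that could affect outcomes | none | IOP outside 8:00 to 10:00 AM |
| Who decides, and when | not stated | no exclusion to decide | not stated |

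The first column resembles the third more than the second. The terms differ (major violation against significant deviation, optional against mandatory) and neither is defined. The match is therefore one of function, not of wording.

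**Step 2. Can the 10.4.1 ITT set serve as written?** Section 10.4.2 defines the primary variable as change from the Visit 2 IOP. Subjects who never received plugs have no such change. For this variable the 10.4.1 set reduces to plugged subjects with Visit 2 and follow-up data, but the plan does not say so and does not make that set primary.

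**Step 3. Does another section close the gap?** Section 14.3 deals with reporting and approving deviations, not with classifying them for analysis. Section 10.4.7 places the final analysis after database closure but does not say that exclusions are settled before IOP is seen.

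**Step 4. Rescue.** Section 7.10.1 calls rescue a protocol deviation and does not say whether it is major. By sections 7.10.1 and 5.4.3.1 the rescued subject is terminated and not replaced. By sections 5.4.2.1(f) and 5.4.3.2 a user of prohibited medication is discontinued and replaced. Since 7.10.1 also calls rescue a prohibited medication, both routes apply on their face and must be reconciled.

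**Step 5. Illustration of size.** Inputs:
- n = 30, the planned maximum.
- Kept subjects at -7 mmHg, near the 7 to 8 mmHg reductions that Appendices I and J report for travoprost drops.
- k = 3 or 6 excluded subjects with mean change m. The documents give no source for k or m, so both are assumptions.
- Every excluded subject has an IOP at the visit analysed.

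Mean with all kept = ((30 - k)(-7) + k·m)/30. The mean with the k excluded is -7.

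- m = -2, k = 3: (27 × -7 + 3 × -2)/30 = -195/30 = -6.5; reduction overstated by 0.5.
- m = -2, k = 6: (24 × -7 + 6 × -2)/30 = -180/30 = -6.0; overstated by 1.0.
- m = -9, k = 3: (27 × -7 + 3 × -9)/30 = -216/30 = -7.2; understated by 0.2.
- m = -9, k = 6: (24 × -7 + 6 × -9)/30 = -222/30 = -7.4; understated by 0.4.

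The shift is k(m + 7)/30, so the assumed m drives it. With m = 0 it would be 0.7 (k = 3) or 1.4 (k = 6). At visits after a subject has left there is no on-treatment IOP to restore, and the choice of set changes nothing there.

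**The case against.** The best defence is that the plan already contains a set that keeps violators. The 10.4.1 ITT set has no violation condition and, for change from Visit 2, reduces to nearly the set one would ask for. This stands, and it makes the repair small. It does not answer the point, because section 10.1 makes a different set primary and gives it the same name.

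A reader might infer that the 10.1 set and the PP set are identical. The documents do not show that. The examples differ, and with only an IOP-timing example the PP set could even exclude less than the 10.1 set. What is established is that the plan does not distinguish them.

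A reader might also infer that rescued subjects will be removed from the primary analysis. Section 7.10.1 does not call rescue a major violation, so this is left open and is not a rule. The disposition conflict may likewise be read as a specific rescue provision overriding a general one, but the text does not say so.

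It is tempting to put a floor on the effect. An eye that enters at 34 mmHg or below and exits above 34 has a positive change, so omitting one such reading would shift a mean of -7 by at least 7/30 = 0.23 mmHg. That is not a general floor. With kept subjects at -4 it is 4/30 = 0.13. Section 7.10.1 also allows rescue because of either eye or for undue medical risk, so the analysed eye need not exceed 34.

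Finally, this is a single-arm pilot with no formal sample size. That limits the consequences but does not settle which set is primary.

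**Conclusion.** The concern holds in this form and should be fixed. Section 10.1 gives an ITT label to a set that works like per-protocol, section 10.4.1 gives the same label to a different set, and exclusions are open-ended, with no decision-maker and no timing. Confidence in this is high, because it rests on the text.

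The size and direction of the effect are unknown. The figures of 0.5 to 1.0 mmHg overstated and 0.2 to 0.4 mmHg understated apply only with 30 subjects, kept subjects at -7 mmHg, 3 to 6 exclusions at the assumed means, and an IOP from every excluded subject at that visit. A reader might infer that the test of the section 10.2 null would change. Nothing here shows that: the illustrated full-set means run from -6.0 to -7.4 mmHg, and it is the estimate that moves.

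**What to change.** Use one definition in sections 10.1 and 10.4.1.

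- **Primary full analysis set:** all subjects with valid consent and HIPAA authorization, plugs inserted in both lower puncta and a Visit 2 IOP. Include those later terminated, discontinued and replaced, or disqualified for improper entry. Remove no subject for a protocol violation or a post-insertion event.
- **Time of day:** keep 8:00 to 10:00 AM as part of the primary variable, as sections 4.2.1 and 10.4.2 have it. Add out-of-window IOPs back in a sensitivity analysis, including an out-of-window Visit 2 IOP, which would otherwise leave a subject without a baseline.
- **PP:** a sensitivity analysis only, with a closed deviation list fixed before database lock and before any look at IOP that depends on exclusions.
- **Readings after events:** state in advance how IOPs taken after rescue, after other prohibited medication or after plug loss are handled, and where an early-exit IOP (section 7.6) counts. Section 5.4 can have terminated subjects followed to Day 90, so such readings may exist. Counting an exit IOP at the next scheduled visit is one option, but it could treat a reading taken after plug extrusion as on-treatment.
- **Missing later visits:** report the number contributing at each visit. Add a sensitivity analysis that carries the last pre-rescue IOP to later visits for subjects terminated for lack of efficacy.
- **Screened set:** use it only for the enrolment and screening-to-baseline endpoints in section 10.4.3.
- **Disposition:** reconcile sections 7.10.1 and 5.4.3.1 with sections 5.4.2.1(f) and 5.4.3.2, and say whether rescue is a major violation for analysis.

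The cost is a paragraph of wording, two sensitivity tables, and an estimate that may become less favourable.
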